### c.1.d Pre and post procedure assessments:

See Table 2.

TABLE 2. Pre- and Post-Procedure Assessments for the VERTPAC-02 Study

Timepoint	Assessment
Pre-procedure	
 
Informed consent
 
Symptom and adverse event monitoring
 
Physical examination (including weight and ECOG performance status)
 
FBC, INR and biochemical profile including tumor markers (CEA/CA19-9), amylase, glucose
 
Pancreatic protocol CT chest, abdomen & pelvis (day -28 to 0)
 
Copy of report of prior histological or cytological proof of PanCa
 
QOL forms (EORTC QLQ30)
 

Post procedure	
 
Following treatment, patients will be monitored closely on the ward. The following protocol will be used to assess patients post treatment
 

Day 2 and 3 after the treatment on Day 1	
 
Symptom and adverse event monitoring, physical examination (including ECOG performance status)
 
FBC and biochemical profile including amylase, glucose
 
Pancreatic protocol CT on day 3, prior to planned discharge
 

Day 14	
 
Symptom and adverse event monitoring, physical examination (including ECOG status)
 
FBC and biochemical profile including amylase, glucose
 
QOL forms (EORTC QLQ30)
 

Months 3, 6 and 12:	
 
Symptom and adverse event monitoring; physical examination (including weight and ECOG status)
 
FBC and biochemical profile including CEA/CA19-9
 
Pancreatic protocol CT
 

Clinical and laboratory assessments will be repeated prior to discharge (anticipated at day 3). All patients will be followed up on day 14 then at three, six and 12 months. At each visit, clinical symptoms will be reviewed, and quality of life and laboratory assessments repeated. In patients in good general condition with evidence of residual tumor or local tumor progression on repeat CT, up to two further PDT treatments may be offered at a minimum of four week intervals. If patients are unable to return for follow up they will be contacted by phone to complete the QOL assessment, as well as asked if they have had adverse events, hospitalization related to disease or progression of disease.

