#### c.1.a Objectives

**Primary:** To show that EUS-guided PDT to the pancreas is effective at direct ablation of advanced or locally advanced and small volume metastatic pancreatic tumors **in a multicenter setting.**

**Secondary:** To evaluate the predictability of tumor necrosis as a function of delivered energy, based on pre-PDT contrast CT scans.

**Tertiary:** Evaluate the safety of chemotherapy given two days after PDT

**Quaternary:** Demonstrate that cancer biomarkers in pre- vs. post-PDT are surrogate markers of response.

**Fig. 4.** Linear echoendoscope with optical diffuser fibre (arrow) extending from a 19G FNA needle.

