## 6.2.2. Protection Against Risk

### ***Adverse Events (Definitions)***

An Adverse Event (AE) is defined as any untoward medical occurrence in a patient or clinical investigation subject administered a pharmaceutical product regardless of the causal relationship with this treatment. Any adverse event or concurrent illness experienced by a patient during any portion of the study will be described in detail, fully evaluated and recorded on an adverse event form in the case report form by the investigator.

An *Unexpected Adverse Event* is defined as an adverse drug event the nature or incidence of which is not consistent with applicable product information.

A *Serious Adverse Event (SAE)* is defined as any untoward medical occurrence that at any drug dose results in:

- Death
- Inpatient hospitalization or prolongation of hospitalization
- A life-threatening event
- Severe or permanent disability
- Cancer (other than cancers diagnosed prior to enrolment in studies involving patients with cancer)
- Congenital anomaly

Note that as defined above, serious events, expected or not, are not necessarily causally associated with the study treatment. Those occurring during treatment and up to one month post-treatment will be reported promptly, and if assessed as a Suspected Unexpected Serious Adverse Reaction (SUSAR) within the timeframes (as specified in the Clinical Trials Regulations 2004) will be reported promptly to the appropriate authorities including the independent Data Monitoring and Ethics Committee (DMEC, see Section 5 below). The ultimate decision for the continuation of the trial lies with the DMEC.

All adverse effects will be assessed for the following:

- Severity (according to NCI toxicity criteria)
- Causality
- Expectedness (see below)
- Seriousness (see above)

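### The phone follow-up asks about hospitalization only if it is related to disease, which is narrower than the plan's serious adverse event criterion, so an admission caused by treatment may be missed

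*Combined protocol and SAP*

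**What the plan says.** The phone contact is described in the paragraph after Table 2 in c.1.d: "If patients are unable to return for follow up they will be contacted by phone to complete the QOL assessment". In the same call they are "asked if they have had adverse events, hospitalization related to disease or progression of disease". No reason for being unable to return is specified, and the documents contain no fuller phone script.

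Section 6.2.2, under Adverse Events (Definitions), defines an adverse event as "any untoward medical occurrence in a patient or clinical investigation subject administered a pharmaceutical product regardless of the causal relationship with this treatment". It adds that "Any adverse event or concurrent illness experienced by a patient during any portion of the study will be described in detail, fully evaluated and recorded". Among the outcomes that make an event serious is "Inpatient hospitalization or prolongation of hospitalization", with no restriction on the reason for admission. The section also notes that "serious events, expected or not, are not necessarily causally associated with the study treatment". Seriousness and causality are listed there as separate assessments. The section on treatment-emergent adverse events gives the drug-related assessment to the investigator.

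The tertiary objective in c.1.a reads "Evaluate the safety of chemotherapy given two days after PDT". Under c.1.b, patients who wish to may start chemotherapy within a week of PDT, after the day 3 CT.

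**The concern.** Whether an event is serious and what caused it are two different questions, and section 6.2.2 keeps them apart. The hospitalization item in the phone call joins them, because it mentions only admissions already linked to the disease. The plan's own list of expected adverse events shows why this matters. Jaundice, cholangitis and duodenal obstruction are placed under cancer progression. Pancreatitis, bleeding and ileus are placed under PDT. Taken literally, the hospitalization item prompts for the first group and not for the second. It also gives no prompt for an admission due to chemotherapy toxicity.

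At stake is how completely serious events are captured in patients followed by phone. A clinic visit includes a physical examination and laboratory tests (Table 2). A phone call does not, so more depends on how the questions are worded. Table 2 lists only day 14 between discharge (expected on day 3) and month 3, while prompt reporting of serious events runs to one month after treatment.

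**Working it through.** The plan gives no figure for this point, so the check compares the texts.

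**1. What is asked.** The call covers adverse events (no qualifier), hospitalization (qualified as disease-related) and progression. The final phrase on progression can be read as a separate topic or as part of the hospitalization qualifier. On either reading the hospitalization item is restricted.

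**2. What counts as serious.** An untoward medical occurrence that results in inpatient hospitalization or its prolongation, with no condition on cause.

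**3. Following an admission through the call.**
- *Admission for jaundice from progression:* prompted directly by the hospitalization item.
- *Admission for pancreatitis after PDT, mentioned by the patient as an adverse event:* recorded under the open question, then classed as serious when the investigator assesses it. Nothing is lost.
- *The same admission, not thought of by the patient as an adverse event:* no item in the call asks for it. It is captured only if another route brings it to light.

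The gap is the third case. The definition of an adverse event is written for investigators, and nothing in the documents says that it is explained to the patient on the phone.

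**4. Direction and size.** The expected number of patients with a missed treatment-caused admission can be written as

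N(phone) × P(treatment-caused admission) × P(not volunteered) × P(not found by another route).

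Each factor is zero or more, so this gap can only lower the count. None of the four is given in the documents. Planned enrolment of 15 + 15 = 30 bounds the first factor between 0 and 30, which is no useful limit. The product cannot be evaluated.

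**5. Link to the stopping rule.** The section on early termination has the monitoring committee consider stopping at 13 or more of 25 patients with a grade 3/4 toxic event. Its stated probability of 0.02 reproduces: P(X ≥ 13 | n = 25, p = 0.30) = Σ C(25,x) · 0.30^x · 0.70^(25−x) for x = 13 to 25 = 0.0175, which rounds to 0.02. The rule counts events by toxicity grade (severity), whereas hospitalization is a criterion of seriousness. A missed admission affects the rule only if it was the sole sign of a grade 3/4 toxic event.

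**The case against.** The strongest reply is that the same sentence begins with an open question on adverse events. Adverse events are defined regardless of cause, must be recorded throughout the study, and are then assessed for seriousness and causality. Pancreatitis and bleeding are on the plan's own list of expected adverse events. The other two topics can be read as additions to the open question. The sentence is also a short summary of topics, not an interview script.

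Most of this stands. A reader might infer that treatment-caused admissions are screened out, with the patient having to judge the cause before being asked. The documents do not support that, because the open question gives such admissions a route into the record. What the reply does not remove is that the one explicit hospitalization prompt is narrower than the criterion it should serve.

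Two further inferences also fail. A reader might take the phone group to be patients too unwell to attend, and hence those most likely to have had a serious event. The plan says only that they are unable to return. A reader might also suppose that a patient who misses day 14 has no other safety contact. Section 6.1.3 gives patients and their GPs an emergency number, the investigators must notify adverse events promptly, other treatments are recorded on the case report form, and c.1.h schedules 4-weekly tumor markers where these were elevated before therapy.

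**Conclusion.** The point holds as a wording mismatch. The phone contact's only hospitalization item is limited to disease-related admissions, while the serious adverse event criterion covers hospitalization whatever the cause. An admission due to PDT, the needle puncture or early chemotherapy may be missed, provided that the patient does not volunteer it as an adverse event and no other route reveals it. Any resulting error would under-count serious events relevant to the tertiary objective.

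Its size cannot be derived from the documents. A reader might infer that missed admissions could move the observed toxicity rate across the plan's 30% limit and so change a stopping decision. That would need an assumed phone share and admission rate, would assume no capture by any other route, and would treat admissions as grade 3/4 toxicity. The rule acts at 13 of 25 patients with graded toxic events (13/25 = 52%), and this gap enters it only indirectly. The point is best labelled a cheap improvement.

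**What to change.** In c.1.d, replace the disease-limited hospitalization item with: *any hospital admission since the last contact, for any reason, with dates and hospital*. Keep the open adverse event question and the progression question. State that the investigator then assesses seriousness and cause under section 6.2.2 (Adverse Events (Definitions) and Treatment-emergent adverse events), using the discharge summary where one can be obtained.

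The cost is one phrase in the protocol and the phone form, requests for discharge summaries, and a few more unrelated admissions to document. The sample size, endpoints and stopping rule are unaffected.

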### Criteria for early termination of the trial

As in our previous trials in this application, a DSMB will monitor toxicity. A grade 3 or 4 toxicity rate of >30% would be considered unacceptable. Therefore, if  $\geq 13$  patients (out of 25) suffer a grade 3/4 toxic event, the DMEC would consider stopping the trial because the likelihood of this occurring by chance alone is 0.02 (statistically significant at the 5% level) if the true toxicity rate were  $\leq 30\%$ .

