#### c.1.b Design of VERTPAC-02 study

This will be a phase II study of 15 (UCL) + 15 (Mayo) patients with histologically proven advanced or locally advanced PanCa or other solid tumors unsuitable for surgical resection. In the first 5+5 patients, EUS guided verteporfin PDT will be used with light delivered at just one site. In the following 10+10 patients, light will be delivered with the fiber at multiple positions, as required to ensure treatment of all appropriate areas of the cancer, as was done in the previous studies with percutaneous fiber insertion. Each patient will be given verteporfin 0.4 mg/kg bodyweight intravenously, followed by light activation 60 minutes after photosensitization (acceptable treatment window 60- 90 minutes). Light delivery will take place via a 5-20 mm length diffuser fiber placed under EUS guidance using red laser light at 690nm. The light dose delivered down the fiber will be fixed at 40 -80 J/cm, which was found to be optimum in our previous VERTPAC-01 study. All patients will be prescribed ciprofloxacin as a prophylactic to reduce the potential risk of infection associated with the fine needle puncture of the tumor. If a patient is allergic to ciprofloxacin, another acceptable broad spectrum antibiotic will be prescribed at the investigators discretion.

Patients will be evaluated by contrast enhanced CT at 2 days after PDT (treatment day 3), and they will be able to commence conventional palliative chemotherapy after that if they so wish within a week of PDT. Patients will also have additional blood draws taken for biomarker analysis before, during, and after their treatment. In previous studies, it was a protocol requirement that chemotherapy

not be given within a month of PDT. However, PDT is a local, one off treatment and chemotherapy is systemic and ongoing. It is an important innovation to give chemotherapy much earlier after PDT as our previous study on PDT for biliary tract cancer showed that delay in giving chemotherapy after PDT put patients at a disadvantage. Treatment response and time to disease progression will be assessed by CT scans at three-monthly intervals, as part of usual practice. Thereafter, patients will continue to be followed up for survival data. Second line chemotherapy and/or re-treatment with verteporfin PDT for progressive disease will be at the discretion of the investigators.

**c.1.c Patient eligibility:** See Table 1.

Inclusion Criteria	Exclusion Criteria

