## **6.5. DATA AND SAFETY MONITORING PLAN**

### ***Data Monitoring and Ethics Committee (equivalent to Data & Safety Monitoring Committee in US)***

The role of the Data Monitoring and Ethics Committee (DMEC) or the Data and Safety Monitoring board (DSMB) is to provide independent oversight on the safety aspects of the trial. The DMEC will also determine the frequency and types of analyses. The committee will meet quarterly to review the data on safety and provide direction on whether a particular trial should continue or be stopped. Upon review of the data, the DMEC or DSMB committee has the power to recommend changes in the experimental protocol, which would additionally be reviewed, or to halt the trial pending further investigation of the data. Halting a trial will trigger an investigation by the Main REC and Sponsor, and the results of the investigation will be reported to the DMEC, TSC, the MHRA and the relevant pharmaceutical

company. A Data Safety Monitoring Committee will also be established at Mayo Clinic Rochester to monitor the study. Should an adverse event occur, it will be reported to both the DMEC and DSMB simultaneously. Should there be any disagreement on a course of action, the most conservative approach with the greatest safety for patients will be followed. (ie perform any recommended diagnostic studies and continue to observe the patient for the longest period recommended)

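### The early-termination section sets one toxicity threshold, 13 of 25, with no earlier look, so the committee has no pre-specified numerical criterion before the 13th affected patient

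*Combined protocol and SAP*

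**What the plan says.** The section Criteria for early termination of the trial sets the standard: "A grade 3 or 4 toxicity rate of >30% would be considered unacceptable". Its trigger is a single count: if 13 or more of 25 patients "suffer a grade 3/4 toxic event, the DMEC would consider stopping the trial because the likelihood of this occurring by chance alone is 0.02". That 0.02 is the tail probability at a true rate of 30% or less, described as significant at the 5% level. The section gives no smaller denominator and no interim look.

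Section c.1.b plans 30 patients (15 at each center) in two stages. "In the first 5+5 patients, EUS guided verteporfin PDT will be used with light delivered at just one site"; the next 10+10 receive light at multiple fiber positions. No numerical toxicity criterion is attached to any point in that sequence.

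Oversight is described elsewhere. In section 6.5, "The committee will meet quarterly to review the data on safety". The same section lets the committee decide how often and in what way data are analyzed, and gives it power to halt. Section 6.2.2 leaves the final decision on continuing with the DMEC.

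**The concern.** A threshold placed under a heading about early termination should give the committee something to apply while the trial is still small. This one does not. At a review after 10 or 12 patients, the only number in the plan is one that cannot yet have been reached.

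This matters because the trial departs from the experience it cites. The phase I report of no serious adverse events comes from percutaneous placement of a single fiber. Here the route changes to EUS, the later stage uses several fiber positions, and chemotherapy may start within a week of PDT, where earlier studies required a month's gap (sections b.1 and c.1.b). If toxicity were high, the gain from a numerical criterion would come early, before most patients had been treated.

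**Working it through.** **Inputs.** Unacceptable rate 30%, threshold 13, denominator 25 and stated tail 0.02 come from Criteria for early termination of the trial. The planned 30 patients and the 10-patient single-site stage come from section c.1.b. True rates of 40%, 50% and 60% are assumptions, because the documents name no rate that the rule is meant to detect.

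**The plan's own figure.** With X binomial, P(X ≥ 13 | n = 25, p = 0.30) = 0.0175, which rounds to the stated 0.02. It is a one-sided exact tail, and it reproduces.

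**Earliest possible trigger.** The count must reach 13, and the single-site stage has 10 patients. Ten affected out of ten has probability 0.30^10 = 0.000006 at a true 30%, yet 10 < 13, so the criterion is not met.

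**Chance that the threshold is met**, P(X ≥ 13 | n, p):

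| True rate | n = 25 (as written) | n = 30 (all planned patients) |
|---|---|---|
| 30% | 0.0175 | 0.0845 |
| 40% | 0.154 | 0.422 |
| 50% | 0.500 | 0.819 |
| 60% | 0.846 | 0.979 |

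Counting 13 over all 30 patients makes the rule more sensitive, but the tail at 30% is then above the stated 5% level.

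**The plan's standard applied earlier.** For each n, take the smallest count r with P(X ≥ r | n, 0.30) ≤ 0.02:

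- n = 10: r = 7, tail 0.0106
- n = 15: r = 9, tail 0.0152
- n = 20: r = 11, tail 0.0171
- n = 25: r = 13, tail 0.0175

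The last is the plan's own threshold.

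**Operating characteristics of the four looks together.** These come from an exact recursion over 30 patients that removes, at each look, the paths that have reached the boundary:

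| True rate | Triggered, four looks | Triggered, 13 of 25 only | Expected patients, four looks |
|---|---|---|---|
| 30% | 0.034 | 0.0175 | 29.5 |
| 40% | 0.206 | 0.154 | 27.3 |
| 50% | 0.559 | 0.500 | 22.4 |
| 60% | 0.872 | 0.846 | 16.7 |

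Expected patients assume that the trial stops when a boundary is met and otherwise runs to 30. At 60%, the first-crossing probabilities at looks 10, 15, 20 and 25 are 0.3823, 0.2475, 0.1526 and 0.0898, leaving 0.1279 that never cross. So 10(0.3823) + 15(0.2475) + 20(0.1526) + 25(0.0898) + 30(0.1279) = 16.7. With one look at 25 it is 25(0.8462) + 30(0.1538) = 25.8. If the 13 events are counted patient by patient up to the 25th, it is 22.0.

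**The case against.** The strongest reply is that stopping does not depend on this count. The committees review safety quarterly, choose their own analyses and can halt; adverse events go to both the DMEC and the Mayo board, and if they disagree the more cautious course is followed (section 6.5). Ten affected patients out of ten would come before people already empowered to act. This stands. A reader might infer that the trial could not be stopped, or that harm would go unnoticed, until 13 patients were affected; the documents do not support that. The threshold itself is advisory.

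A second reply is that the low sensitivity at 40% rests on a rate the reviewer chose, on n = 25, and is hardly cured by earlier looks. This also stands: four looks still fail to trigger in 79% of trials at 40% (1 − 0.206). If 13 is counted over all 30 patients, the existing count triggers more often than the four looks at 40%, 50% and 60%, at the price of 8.4% false triggering at 30%.

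A reader might also note that 12 of 25 has a tail of 0.044 at 30% and conclude that the rule misses its own 5% level. It does not: the plan chose a stricter cut and reported its tail correctly.

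These replies do not supply an early criterion. Discretion to halt is not a stated standard for when to consider halting, and the section offers none before 13 events.

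**Conclusion.** The point holds as a gap in pre-specification. The plan's only numerical toxicity criterion cannot be met during the single-site stage, whatever happens in it. This follows from the count alone and needs no assumed toxicity rate.

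The sensitivity figures do need assumptions: independent patients with a common rate, a denominator of 25, and true rates that the plan does not supply. They describe the rule; they do not show that it fails a target, since no target is stated. The practical gain from earlier looks is speed when toxicity is high, not better detection of a modest excess over 30%. The section contains no arithmetic error and independent oversight exists, so this is an inexpensive improvement that should be made, not a flaw that invalidates the design.

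**What to change.** Apply the plan's existing standard (30%, tail at most 0.02) to the pooled count across both centers at successive looks at which the DMEC would consider stopping. The boundaries 7 of 10, 9 of 15, 11 of 20 and 13 of 25 illustrate this; the sponsor and DMEC should set the final looks and boundaries. Keep the advisory wording and the committees' discretion. Nothing here proposes a condition for moving from single-site to multiple-position treatment.

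Beside the rule, state its operating characteristics: the chance of triggering at 30%, 40%, 50% and 60%, including the low figure at 40%, and the expected number treated. State which patients the denominator covers, and reconcile 25 with the 30 planned, because the properties of a count of 13 change with it.

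The cost is protocol wording, and quarterly meetings are already scheduled. The statistical price is false triggering at a true 30% of 3.4%, up from 1.7% and still below 5%.
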